## 4.2 STUDY ENDPOINTS

## 4.2.1 PRIMARY ENDPOINT:

To determine if sildenafil administration improves CBF/CVR, reduces symptoms, and improves cognitive performance in concussed boxers/MMA fighters. Hypothesis: Both single and multiple sildenafil therapy improves CBF/CVR, symptoms, and cognition in concussed boxers. Also, long-term administration of daily doses of sildenafil to concussed boxers/MMA fighters is well tolerated. Following injury, we will enroll 100, active boxers/MMA fighters and 80, controls into a double-blind, placebo-controlled study. At a 1:1 ratio, the subjects will receive a single treatment of either placebo or sildenafil. The purpose of this study is to determine if sildenafil treatment improves CBF/CVR, reduces symptoms, and improves cognitive outcomes. In this study we will treat the injured athletes once (within 2 hours of injury) or daily (for 14 days) to determine if sildenafil improves outcomes. Previous clinical studies conducted by our research group, we found that sildenafil treatment (60mg) is tolerable within the TBI population. The athletes will maintain a daily diary of symptoms. At day 1-3 and 30 after injury, the CBF/CVR MR imaging procedures, the Rivermead Post Concussion Symptom Questionnaire, and neuropsychological assessments (NIH Common Data Elements) will be conducted to study the effect of sildenafil therapy. Blood (8cc) and saliva will also be collected to measure brain biomarkers of injury. Tolerability (blood testing and symptom reporting) assessments will be conducted throughout the study to ensure that the symptomatic boxers tolerate multiple, daily doses of sildenafil.

#### 4.2.1.a. MRI

#### Preparation for the MRI procedure:

At baseline and post-concussion time-points (day 1-3, 30), the research coordinator will schedule the imaging procedure with the subject. There will be a 3-day window to facilitate scheduling of the MRI studies. Once the subject arrives to UT Southwestern Medical Center (Dallas, Texas), the research coordinator will escort the participant to the Advanced Imaging Resource Center for the MR imaging session. Prior to conducting the imaging procedures, the subjects will be screened for MRI safety using the Screening Questionnaire. The subjects may be asked to lie still for up to 7-10 minutes at a time. While in the scanner they will hear loud knocking noises, and they will be fitted with earplugs or earmuffs to muffle the sound. They will be able to communicate with the MRI staff at all times during their scan, and they may ask to be moved out of the machine at anytime. Participants will first have a structural MRI scan.

The structural MRI sequences we will use do not require contrast. The subjects will not be required to do any tasks during the structural MRI. Sequences used for the structural MRI include T1 Magnetization Prepared Rapid Gradient Echo (MPRAGE), Fluid Attenuated Inversion Recovery (FLAIR), Diffusion Tensor Imaging (DTI), resting state functional connectivity (rfMRI), diffusion weighted imaging (DWI), Arterial Spin

Labeling (ASL) to assess resting CBF, gradient echo (GRE) and/or T2\* susceptibility weighted imaging (SWI). If image quality of a given sequence is inadequate due to patient motion for example, these may be repeated at the discretion of the MRI technologist or radiologist. The structural scan takes approximately 45 minutes.

#### The BOLD sequence with hypercapnia challenge:

The participants will have a BOLD MRI scan (baseline, day 1-3, and 30 after injury) with CVR hypercapnia measurements. Global and region-specific CVR will be assessed using hypercapnia induced by breathing 5% carbon dioxide (CO2) mixed with 21% O2 and 74% N2. Study participants will be taken out of the scanner after the initial 45-minute structural scan and fitted with a breathing mask that covers the mouth and nose (similar to a C-PAP mask). After

the mask is in place, the patient is placed back into the magnet. Hypercapnia will be induced via a Douglas bag fitted with a valve to switch between room air and 5% CO2. A research assistant will be inside the magnet room throughout the BOLD scan with hypercapnia challenge to switch the valve and monitor the subject. Physiologic parameters, including end-tidal (EtCO2), breathing rate, heart rate, and capillary oxygenation will be monitored continuously during the experiment using a capnograph and pulse oximeter. The type of gas breathed is switched every minute similar to a block design fMRI experiment, while Blood Oxygen Level Dependent (BOLD) MRI Images are acquired for 7 minutes.

Times are close approximations which may be altered depending on the cooperation of the patient. The subject will not engage in the hypercapnia challenge for more than the specified 7 min. Total scan time with structural and BOLD sequences will be approximately 1 hour.

#### MRI patient procedures:

- 1. Safety screening
- 2. 45 min structural scan
- 3. Out of the magnet and fitted with the mask for hypercapnia challenge
- 4. 7 min. BOLD scan with mask and hypercapnia

#### 4.2.1.b. TBI Neuropsychological Assessments

In this clinical study, we test whether sildenafil improves cognitive, mood, and functional outcomes in injured boxers. The testing procedures will be conducted in a quiet room at UTSWMC by a neuropsychologist or trained coordinator. We anticipate that the testing procedures will take approximately 1 hour to complete. The subjects will be given frequent rests and they have the right to refuse to answer any questions or to stop a test at any time and for any reason. TBI phenotyping instruments recommended for evaluation in all TBI cohort or natural history studies have been labeled the TBI Common Data Elements (CDEs)(58). The subject will be interviewed, complete questionnaires, take pen-and-paper tests, and perform simple actions.

In this study we will include the following selected subset of assessments taken from the CDE's:

- Hopkins Verbal Learning Task (HVLT). The **Hopkins Verbal Learning Test** (HVLT) is a brief verbal learning and memory test with six alternate forms of 12 words.
- The Sport Concussion Assessment Tool (SCAT5), from the Concussion in Sport Group, is a standardized tool for evaluating injured athletes for concussion and can be used in athletes aged 13 years and older. This test will take approximately 30 minutes.
- Satisfaction with Life Scale (SWLS): is a short 5-item instrument designed to measure global cognitive judgments of satisfaction with one's life. The scale usually requires only about one minute of a respondent's time.
- Rivermead Post-Concussion Symptom Questionnaire: rate the severity of 16 different symptoms commonly found after a TBI (5 min).
- Galveston Orientation and Amnesia Test (GOAT)-modified for sports athletes

## 4.2.2 SECONDARY ENDPOINT:

To determine if sildenafil reduces the blood/saliva levels of brain biomarkers of iniury after concussion. The goal of this study is to produce pilot efficacy data to design a definitive study aimed at testing the efficacy of the administration of sildenafil at reducing the blood/saliva levels of Von willebrand factor (vWF), glial fibrillary acidic protein (GFAP), neurofilament-H (NFL-H), creatine kinase-B (CKBB) and tau. In brief, about 8cc of blood and saliva will be collected at each time-point. The blood and saliva will be collected once at baseline and on day 1-3 and 30 after injury. Upon collecting the samples, the blood will be centrifuged at 4 degrees Celsius for 10 minutes at 1500 rpm. The plasma/saliva will be collected and aliguoted into 1 ml tubes and immediately frozen at -80 degrees Celsius. To measure the levels of brain biomarkers, the plasma levels of vWF, GFAP, NFL-H, CKBB, and tau will be measured using the enzyme-linked immunoassay according to the manufacturer's instructions. Each sample will be loaded onto the 96-well plate in triplicate. Each sample will be tested in triplicate. The plate will be incubated for 2 h at room temperature, washed, and 200 µl of the substrate will be added for 90 min at room temperature. After 90-min, the absorbance will be detected at 405 nm. The values will be compared to the standard curve and the concentration of the biomarker will be determined.

## 5 STUDY ENROLLMENT AND WITHDRAWAL

## 5.1 PARTICIPANT INCLUSION CRITERIA

## FOR ATHLETES

- 1. Age 18-35
- 2. Male or female professional boxers/MMA fighters
- 3. Ability to undergo MR imaging procedures
- 4. At least one of the following:
  - a. KO/TKO scored by fight referee.
  - b. Greater than 25 blows to the head.
- Significant post-concussive symptoms (Symptom Score > 1 on at least 3 items from the Rivermead Post-Concussion Questionnaire)
   FOR CONTROLS
- 1. Age 18-35
- 2. Male of female who do not participate in contact sports
- 3. Screen negative for mTBI using Ohio State TBI ID

## 5.2 PARTICIPANT EXCLUSION CRITERIA

- 1. Contraindication to sildenafil which includes the following:
  - a. Current use of organic nitrate vasodilators
  - b. Use of ritonavir (HIV-protease inhibitor)
  - c. Current use of erythromycin, ketoconazole, or itraconazole

STU032018-063, [name], FormA-ResearchProtocol, Mod\_6, 11-25-19 (1) NIH-FDA Clinical Trial Protocol

- d. Current use of cimetidine
- e. Current resting hypotension (BP < 90/50 mm Hg)
- f. Current severe renal insufficiency (Creatinine Clearance < 30mL/min)
- g. Current hepatic cirrhosis
- h. Current cardiac failure or coronary artery disease causing unstable angina
- i. Retinitis pigmentosa
- j. Known hypersensitivity or allergy to sildenafil of any of its components
- 2. Daily therapy with a PDE5 inhibitor within the past 2 months
- 3. Immediate hospitalization for severe concussion
- 4. History of neurological or psychiatric disorder not related to TBI
- 5. Known inclusion in another interventional clinical trial
- 6. Subjects with metal implants that would interfere with the MR imaging procedures
- 7. Sickle cell disease
- 8. History of priapism

# 5.3 STRATEGIES FOR RECRUITMENT AND RETENTION

Within the North Texas area there are approximately 130 boxing training centers. Over the last 6 years we have built relationships with trainers at these facilities and about 125 boxers have previously been enrolled in both observational and interventional studies conducted by the [name] laboratory. We have been successful with enrolling athletes (boxers, MMA fighters, etc.) and completing the clinical studies with a very low dropout rate (10%). Thus, we believe that will meet study recruitment and experience very little dropouts.Our target sample size is 100 athletes. We will also recruit 80 healthy controls.

# 5.4 PARTICIPANT WITHDRAWAL OR TERMINATION

# 5.4.1 REASONS FOR WITHDRAWAL OR TERMINATION

In this study, the participants will be allowed to withdraw at any point. Also, the PI and/or study investigators may choose to withdraw a participant at any time. The reason for withdrawing participants may be for administrative purposes, non-compliance, and/or medical reasons.

## 5.4.2 HANDLING OF PARTICIPANT WITHDRAWALS OR TERMINATION

If a subject withdraws or is withdrawn from the study, any remaining unused samples and/or data identified as theirs will be destroyed at their request. If the PI or study investigators do not receive a request, then the samples will continuue to be used in the analysis as applicable.

# 5.5 PREMATURE TERMINATION OR SUSPENSION OF STUDY

Version 2.0 1 April 2018

Drs. [name] and [name], who are the medical monitors, have the authority to halt the study, remove individual subjects from the study, and take whatever steps are necessary to protect the safety and well-being of research subjects. An independent monitor from UTSWMC will also have the capability to stop a study for safety reasons.

The medical monitors, PI, Independent monitor, and IRB will assess the measures taken by the study team in response to safety issues that caused the study to be stopped or suspended. Revised safety measures taken by the study team will be in a written report submitted to the medical monitor, UTSWMC monitor and IRB of record. Only when these entities agree in writing that the problems have been satisfactorily addressed, the protocol may be re-activated.

# 6 STUDY AGENT

# 6.1 STUDY AGENT(S) AND CONTROL DESCRIPTION

# 6.1.1 ACQUISITION

Sildenafil (60mg) and placebo tablets will be ordered from Pfizer and delivered to the UTSWMC pharmacy. The UTSWMC pharmacy will be responsible for packaging the study drug and devising the randomization schedule.

# 6.1.2 FORMULATION, APPEARANCE, PACKAGING, AND LABELING

Sildenafil is supplied as blue, film-coated, rounded-diamond-shaped tablets containing sildenafil citrate equivalent to 60 mg of sildenafil. The placebo pills will be compounded and have similar appearance to the investigational drug.

# 6.1.3 PRODUCT STORAGE AND STABILITY

The drug will be stored at room temperature (25°C [77°F]) with excursions permitted (59-86°F).

## 6.1.4 PREPARATION

The study drug is in pill format. The participant will self administer the sildenafil pill. The study participant will maintain a daily diary to document the administration of the study drug.

# 6.1.5 DOSING AND ADMINISTRATION

STU032018-063, [name], FormA-ResearchProtocol, Mod\_6, 11-25-19 (1) NIH-FDA Clinical Trial Protocol

In the first and second group, the participants will be administered either a single-dose or 14 pills of placebo or sildenafil (60mg) after suffering a concussion. The first dose will be taken at 2hours after injury.

## 6.1.6 ROUTE OF ADMINISTRATION

Oral

# 6.1.7 DOSE ADJUSTMENTS/MODIFICATIONS/DELAYS

N/A

# 6.1.8 DURATION OF THERAPY

The duration of the study for the primary and secondary endpoints will be 30 days.

# 6.1.9 TRACKING OF DOSE

During the course of this study, the participant will maintain a drug diary and document when the treatment was administered. Once the participant completes the study, the pill bottle will be collected and the remaining pills in each bottle will be counted.

# 6.1.10 DEVICE SPECIFIC CONSIDERATIONS

N/A

## 6.2 STUDY AGENT ACCOUNTABILITY PROCEDURES

The UTSWMC pharmacy will create the randomization schedule. The study coordinator will follow the randomization schedule and deliver the pill bottles to the participant. Instructions will be given the research subject pertaining to daily documentation of drug administration and returning the pill bottles at the completion of the study.

## 7 STUDY PROCEDURES AND SCHEDULE

## 7.1 STUDY PROCEDURES/EVALUATIONS

## 7.1.1 STUDY SPECIFIC PROCEDURES

Prior to performing any study procedures, consent will be obtained. All of the evaluations and procedures will performed for research purposes only. None of the tests will be for clinical purposes. In table 2, the study procedures are listed for the athletes that will be treated with sildenafil after competition and procedures for the controls.

Boxers (n=100); Controls (n=80)	Baseline	Day 1-3	Day 7 (phone)	Day 15 (phone)	Day 22 (phone)	Day 30
1. Inclusion/Exclusion Criteria	Х					
2. Informed Consent	Х					
3. Blood/saliva collection (side effects, tolerability, brain biomarkers)	Х	Х				х
4. Structural MRI (T1 MPRAGE, FLAIR, DTI, rsBOLD)	х	Х				Х
5. Randomization		Х				
6. Dispensing study drug (sildenafil or placebo)		Х				
7. Pill counting for compliance						Х
8. Monitoring for adverse effects		Х	Х	Х	Х	Х
9. Symptom inventory		Х	Х	Х	Х	Х
10. Neuropsychometric CDEs	Х	Х				Х

## 7.1.2 STANDARD OF CARE STUDY PROCEDURES

N/A

## 7.2 LABORATORY PROCEDURES/EVALUATIONS

## 7.2.1 CLINICAL LABORATORY EVALUATIONS

#### Biochemistry:

Blood (~8cc) will be collected and the blood albumin, alkaline phosphatase, total bilirubin, bicarbonate, BUN, calcium, chloride, creatinine, glucose, LDH, phosphorus, potassium, total protein, SGOT [AST], SGPT [ALT], sodium, and coagulase levels will be measured from from the participants at day 1-3 and 30 after injury. By performing these tests we will be able to detect side effects that may be associated with the study drug. For example, if the AST or ALT ratio is out of the normal range, the participant(s) will be withdrawn from the study. Also, if the participant reports any side effects that may be linked to the study drug, the study participant will be withdrawn from the study. The IRB and FDA will be notified within 7 business days. The

testing will be performed by Quest diagnostics, Dallas, Texas. Blood will also be collected to measure the levels of brain biomarkers of injury within the athletes.

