The participants in **group 1** (single therapy) will consist of the active boxers/MMA fighters that experience significant sub-concussive blows or a concussion during competition. In this group, 65, professional male/female boxers/MMA fighters within the North Texas region will be screened and about 50 concussed athletes will be enrolled. The athletes that have at least 25 blows to the head and a Symptom Score > 1 on at least 3 items from the Rivermead Post-Concussion Questionnaire following their fight will be enrolled in this study. The research subjects will be treated with sildenafil (60mg), once at 2 hours after experiencing a concussion.

**Group 2** will consist of the active boxers/MMA fighters that experience significant subconcussive blows or a concussion during competition. In this group, 65, professional male/female boxers/MMA fighters within the North Texas region will be screened and about 50 concussed athletes will be enrolled. The athletes that have at least 25 blows to the head and a Symptom Score > 1 on at least 3 items from the Rivermead Post-Concussion Questionnaire following their fight will be enrolled in this study. Once enrolled, the subjects will be treated with sildenafil (60mg) once-a-day for 14 days.

**Healthy Control group:** In this study, 80, age (between 18 and 35)-matched healthy controls will be enrolled. The control subjects will participate in neuropsychological testing, blood/saliva collection, and the MR imaging procedures. Healthy controls will be tested in group 1 (n=40) and 2 (n=40) and randomized to receive either sildenafil or placebo in this group.

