#### Follow-up Visit (Visit 3, Day 1-3)

- Record adverse events
- Collect blood/saliva for biochemistry, biomarker testing
- Administer sildenafil or placebo (once)
- MRI procedures
- Neuropsychological testing

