# 8.3 TIME PERIOD AND FREQUENCY FOR EVENT ASSESSMENT AND FOLLOW-UP

After enrollment into the study, a telephone follow-up will occur every 7 days. Telephone followup and clinic visits will give physician investigators an opportunity to interface with participants. Participants will be instructed to call 911 or go to the nearest emergency room in the event of a serious symptom. Investigators will carry a pager and will be available to the study participants for questions or conserns about side effects. Study participants will be cautioned against taking medications that may have possible adverse interactions with sildenafil. Licensed physicianinvestigators may prescribe medication for headache or other minor side effects. Otherwise, patients will be instructed to seek medical attention from their personnal physician.

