## 8.4 REPORTING PROCEDURES

## 8.4.1 ADVERSE EVENT REPORTING

Adverse events will be reported in accordance with Federal requirements. All adverse events, serious and non-serious, expected and unexpected, related and unrelated will be tracked by the study coordinator and medical monitors. Serious or unexpected adverse events and other unanticipated problems will be reported orally as soon as possible and in writing within 7 days if life-threatening and within 15 days otherwise to the IRB and FDA. Expected or non-serious adverse events will be reported at the time of continuing review.

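### Section 7.2.1, as written, removes anyone with a possibly drug-linked side effect from the study, not only from drug, so Day 30 outcomes are lost, probably more often on sildenafil

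*Combined protocol and SAP*

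**What the plan says.** Section 7.2.1 (Biochemistry) contains two mandatory withdrawal triggers. The first is laboratory: "if the AST or ALT ratio is out of the normal range, the participant(s) will be withdrawn from the study". The second is symptomatic: "if the participant reports any side effects that may be linked to the study drug, the study participant will be withdrawn from the study". It then adds: "The IRB and FDA will be notified within 7 business days".

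Other sections bear on the same participants:

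- **5.4.1** makes withdrawal by the investigators discretionary, with medical reasons as one ground.
- **5.4.2** covers only what is already held: "any remaining unused samples and/or data identified as theirs will be destroyed at their request". Without such a request, the material stays in use.
- **7.3.3** describes a final visit if the study ends early. Cognitive tests, symptoms and MRI are required only after day 10.
- **8.3** says physician-investigators "may prescribe medication for headache or other minor side effects".
- **8.4.1** says: "Expected or non-serious adverse events will be reported at the time of continuing review".
- **Section 9** adds a blood sample and medical monitoring after an unexpected event, but no outcome assessments.
- **10.1** promises an intention-to-treat analysis of all available data and assumes missing at random. It plans a Fisher's exact comparison of missingness by arm, imputation, and shared-parameter and pattern-mixture models.

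On dosing, section 4.1 says of group 1: "The research subjects will be treated with sildenafil (60mg), once at 2 hours after experiencing a concussion". The Visit 3 list in 7.3.2 nevertheless has the entry "Administer sildenafil or placebo (once", and the 7.1.1 schedule puts randomisation and dispensing at Day 1-3.

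**The concern.** Stopping the drug and leaving the study are different events, and 7.2.1 merges them. The trigger is any side effect that might be linked to drug, however mild. Side effects are asked about at Day 1-3, by phone at Days 7, 15 and 22, and at Day 30, so reports will be elicited. Someone removed before Day 30 contributes no Day 30 MRI, symptom or cognitive result, and an early report could also cost the Day 1-3 visit.

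The Day 30 two-sample comparisons would then be made in people selected by an event that happens after randomisation and that the protocol's own Table 4 shows is commoner on sildenafil. Randomisation no longer protects that comparison. The rule also ends observation of tolerability at the first complaint, although 4.2.1 hypothesises that daily sildenafil is well tolerated.

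For many participants, withdrawal would change data collection and not exposure. In group 1 the single dose has already been taken, unless the Visit 3 entry means a further tablet. In group 2 the 14 doses are finished by the Day 22 call. They are finished by the Day 15 call only if dosing began 2 hours after injury: dispensing at Day 1-3 would carry it to about Day 14-16.

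**Working it through.** **Inputs.** Table 4 (8.2.2), sildenafil v placebo: headache 16% v 4%, flushing 10 v 1, dyspepsia 7 v 2, nasal congestion 4 v 2, urinary infection 3 v 2, abnormal vision 3 v 0, diarrhoea 3 v 1, dizziness 2 v 1, rash 2 v 1. Table 7 (three times daily for 12 weeks), headache: 27/70 (39%) on placebo v 32/69 (46%), 28/67 (42%) and 35/71 (49%) on sildenafil. Section 10.1: 50 per arm, CVR difference 0.86, correlation 0.2. Section 10.2.1: 10-20% dropout, not split by arm.

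**The plan's own figure.** The SD of change is √(2(1 − 0.2)) = 1.265. With df = n_s + n_p − 2 and noncentrality 0.86 / (1.265 √(1/n_s + 1/n_p)), 50 per arm gives 0.86 / (1.265 × 0.2) = 3.40 on 98 df. Two-sided 5% power is 92%, not the stated 80%; 80% needs 35 per arm. This mismatch is a separate matter, and 92% is used here as the no-loss reference. It pools the two regimens, which the plan does not specify. Within one regimen (about 25 per arm) the same formula gives about 65% before any loss.

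**Loss by arm.**

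- Headache only: 0.16 × 50 = 8 v 0.04 × 50 = 2.
- All nine Table 4 events, independent: 1 − 0.84 × 0.90 × 0.93 × 0.96 × 0.97³ × 0.98² = 0.408 v 1 − 0.96 × 0.99⁴ × 0.98³ = 0.132.
- All nine, no overlap: the percentages sum to 50% v 14%.
- Table 7 headache: 42-49% v 39%.

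**Power on those remaining**, same formula. For headache only, 42 v 48 remain: 0.86 / (1.265 √(1/42 + 1/48)) = 3.22 on 88 df, giving 89%.

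| Scenario | Withdrawn, sildenafil v placebo | Gap (points) | Overall | Left of 50 v 50 | Power |
|---|---|---|---|---|---|
| No loss | 0 v 0 | 0 | 0 | 50 v 50 | 92% |
| Table 4, headache only | 16% v 4% | 12 | 10% | 42 v 48 | 89% |
| Table 4, nine independent | 41% v 13% | 28 | 27% | 30 v 43 | 80% |
| Table 4, no overlap | 50% v 14% | 36 | 32% | 25 v 43 | 76% |
| Table 7, headache only | 42-49% v 39% | 3-10 | 40-44% | 25-29 v 31 | 70-73% |

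The two tables pull in different directions: Table 4 gives the larger imbalance, Table 7 the larger total loss. Only the headache-only Table 4 case fits within the 10-20% dropout allowance.

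**Bias.** Let withdrawn participants differ from retained ones by k SD, equally in both arms. Each retained mean is the arm mean minus w·k, so the bias has size k(w_s − w_p). For each 0.1 SD of k this is 0.012 SD (headache only), 0.028 (nine independent), 0.036 (no overlap) or 0.003-0.010 (Table 7). The documents give no value for k. With k = 0 the bias is zero. In the headache-only case it is also zero if only the background 4% are prognostically different and the drug-caused extra 12% are not.

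**Does anything restore Day 30?** Section 5.4.2 preserves only earlier data. Section 7.3.3, even if read per person, gives an assessment at exit after day 10, not at Day 30, and requires no MRI, symptom or cognitive assessment for earlier leavers. Section 8.3 implies that people with minor effects stay, but does not override 7.2.1. Section 9 adds safety tests only. Intention to treat on available data cannot include what was never collected.

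**The case against.** The strongest reply is that 7.2.1 is a loosely worded safety sentence rather than a settled design choice. Section 5.4.1 is discretionary, 8.3 foresees treating headache, and 8.5 halts dosing only after three grade 3 events judged probably related. Staff may apply the rule only to unexpected events, the kind that section 9 reports within 7 business days. Section 7.3.3 counts days from injury and enrolment, so reading it per person is natural. Practice may therefore be milder than the text. That stands, and it limits the size. It does not remove the problem, because unwritten discretion over who leaves is itself a source of selective loss.

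A second reply is that 10.1 already plans for missing data. Day 1-3, diary and phone data do allow a partial comparison of withdrawn and retained participants. The planned models, however, rest on assumptions about unseen Day 30 values that cannot be tested, and Fisher's test has only about 37% power to detect 16% v 4% missingness at 50 per arm.

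Some stronger readings are tempting but not supported:

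- *The AST/ALT trigger also removes more sildenafil participants.* Table 5 lists abnormal liver tests among events equally common on placebo, and Table 4 has no liver row.
- *The 7-business-day notice flatly contradicts 8.4.1.* It may mean notice of a withdrawal rather than of an adverse event, so it is a secondary inconsistency at most.
- *No group 2 participant has drug left at the Day 15 call.* That depends on whether dosing began 2 hours after injury.

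**Conclusion.** The point holds for the rule as written. Section 7.2.1 ends study participation for any possibly drug-linked side effect and for out-of-range AST/ALT, and no section returns these people to Day 30 assessment. For reported side effects, the loss is expected to be commoner on sildenafil.

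The size is uncertain. If every listed event in a scenario triggered withdrawal, overall loss would be 10% to 44%, the arm gap 3 to 36 points, and pooled power about 89% down to 70%. Loss would be below this range if staff acted only on unexpected events. Both tables come from other populations and schedules, and half the athletes take a single dose. Concussed placebo participants may also report headache, which would narrow the gap while raising the total.

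A reader might infer that the rule biases the trial for or against sildenafil. The documents do not support this: the direction depends on an outcome gap they do not give, and the bias may be zero, leaving only lost precision. Nor is power the main argument. The case for change is that primary-endpoint data would be lost avoidably and for a treatment-related reason. This should be fixed; confidence is medium.

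**What to change.** Reword 7.2.1 so that a side effect or abnormal AST/ALT may stop study drug but does not by itself end study participation. Participants who have not withdrawn consent keep the scheduled calls and the Day 1-3 and Day 30 assessments, and are analysed in their assigned arm. Except any procedure that an investigator or medical monitor judges unsafe, and leave unchanged the medical monitors' power to remove subjects (5.5) and the pregnancy rule (8.4.2). When to stop drug remains the sponsor's decision.

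Record drug discontinuation, with its date and reason, as a tolerability outcome. State whether 7.3.3 applies to individuals. Reconcile 7.2.1 with 5.4.1, 8.3 and 8.4.1.

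With side-effect withdrawals removed, 50 v 50 remain before ordinary dropout. The cost is a protocol amendment and continued follow-up of participants who are off drug. The visits and calls are already in the 7.1.1 schedule; the documents give no budget, so no cost figure is offered.
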